## 12. DATA ANALYSIS

Data will be handled and processed according to Celerion Standard Operating Procedures, which are written based on the principles of GCP.

### 12.1 Statistical Analysis

Detailed methodology for summary and statistical analyses of the data collected in this trial will be documented in a Statistical Analysis Plan (SAP). The SAP will be prepared by Celerion and agreed upon with the Sponsor. This document may modify the plans outlined in the protocol; however, any major modifications of the primary endpoints definition and/or its analysis will also be reflected in a protocol amendment. Additional statistical analyses other than those described in this section may be performed if deemed appropriate and included in the SAP.

#### 12.1.1 Sample Size Calculation

The sample size chosen for this study was selected without statistical considerations. It has been determined adequate to meet the study objectives. Cohort 1 with 6 subjects (4 active and 2 placebo) and Cohorts 2, 3, and 4 with 5 subjects (4 active and 1 placebo) are sufficient to characterize the single-dose safety, tolerability, and PD profile.

#### 12.1.2 Subjects to Analyze

Safety population: All subjects who received the study drug (active or placebo) will be included in the safety summary.

PD population: All subjects receiving the study drug (active or placebo) and having any measurable PD data will be included in the PD data set. The Sponsor will assess the real-time aPTT on-site, and also evaluate protein C.

#### 12.1.3 Safety Analysis

The following analyses will be performed; however no formal inferential statistics will be done on safety assessments.

The placebo subjects from all cohorts will be pooled into a single placebo group for all summaries and presentations.

Descriptive statistics will be calculated for quantitative safety data and frequency counts will be compiled for classification of qualitative safety data, as appropriate.

#### **Adverse Events:**

AEs will be coded using the most current version of MedDRA® available at Celerion.

A by-subject AE data listing, including verbatim term, preferred term, treatment, severity, and relationship to drug, will be provided.

The number of subjects experiencing TEAEs and number of TEAEs will be summarized by dose level using frequency counts.

Injection site reaction will be assessed.

**Medical History and Physical Examination:**

Medical history will be listed by subject.

Changes in physical examinations will be described in the text of the final report.

**Clinical Laboratory Results, Electrocardiograms, and Vital Signs Measurements:**

All clinical laboratory results, 12-lead ECGs, vital signs measurements, and their change from baseline, will be summarized by dose level and time point of collection.

A shift table describing out-of-normal range shifts will be provided for clinical laboratory results.

Thrombin time will be assessed.

**Concomitant Medications:**

Concomitant medications will be listed by subject.

**Immunogenicity:**

ADA detection will be reported and summarized descriptively.

**12.2 Pharmacodynamics**

**12.2.1 Pharmacodynamic Parameters**

APC-PCI values will be listed and presented graphically.

**12.2.2 Statistical Methods for Pharmacodynamic Analyses**

The placebo subjects from all cohorts will be pooled into a single placebo group for all summaries and presentations.

Individual, mean, and median data APC-PCI values, will be presented graphically for all treatments.

Additional analyses may be performed as deemed necessary upon review of the data.

**12.3 Assessment of Pharmacokinetics**

Pharmacokinetics will not be assessed in this study.

## **13. STUDY ADMINISTRATION**

### **13.1 Ethics**

#### **13.1.1 Institutional Review Board**

This protocol will be reviewed by the Advarra IRB, and the study will not start until the IRB has approved the protocol or a modification thereof. The IRB is constituted and operates in accordance with the principles and requirements described in the US Code of Federal Regulations (21 CFR Part 56). The IRB is compliant to International Council on Harmonisation (ICH) guidelines, and may be reached at:

Advarra IRB  
[name]  
[name]  
[contact]

#### **13.1.2 Ethical Conduct of the Study**

This research will be carried out in accordance with the protocol, US Code of Federal Regulations, 21 CFR Parts 50, 56, and 312, the ethical principles set forth in the Declaration of Helsinki, GCP, and the ICH harmonized tripartite guideline regarding GCP (E6 Consolidated Guidance, April 1996).

#### **13.1.3 Subject Information and Consent**

The purpose of the study, the procedures to be carried out and the potential hazards will be described to the subjects in non-technical terms. Subjects will be required to read, sign and date an ICF summarizing the discussion at screening, and will be assured that they may withdraw from the study at any time without jeopardizing their medical care.

Subjects will be given a copy of their signed ICF.

### **13.2 Termination of the Study**

The Sponsor reserves the right to discontinue this study and Celerion reserves the right to terminate the study in the interest of subject welfare, at any time.

### **13.3 Data Quality Assurance**

Standard operating procedures are available for all activities performed at Celerion relevant to the quality of this study. Designated personnel of Celerion will be responsible for implementing and maintaining quality assurance (QA) and quality control systems to ensure that the trial is conducted, and that data are generated, documented and reported in compliance with the study protocol, GCP and GLP requirements as well as applicable regulatory requirements and local laws, rules and regulations relating to the conduct of the clinical study.

The Clinical Study Report will be audited by the QA department and the QA audit certificate will be included in the study report.

All clinical data will undergo a 100% quality control check prior to clinical database lock. Edit checks are then performed for appropriate databases as a validation routine using SAS® to check for missing data, data inconsistencies, data ranges etc. Corrections are made prior to statistical database lock.

### **13.4 Direct Access to Source Data/Documents**

The PI must maintain, at all times, the primary records (i.e., source documents) of each subject's data. Examples of source documents are laboratory reports, drug inventory, study drug label records, and CRFs that are used as the source.

Celerion will ensure that the Sponsor, IRB and inspection by domestic and foreign regulatory authorities will have direct access to all trial-related sites, source data/documents, and reports for the purpose of monitoring, auditing (ICH[E6] 5.1.2 & 6.10) and inspection. In the event that other trial-related monitoring should be done by other parties, they will be required to sign a confidentiality agreement prior to any monitoring and auditing.

### **13.5 Study Supplies**

The Sponsor will supply sufficient quantities of E-WE thrombin and the placebo to allow completion of this study. The lot numbers, manufacture dates, and expiration dates (if available) of the drugs supplied will be recorded in the final report.

The investigational product(s) will be shipped to a designee at the study site and must be stored in a pharmacy or locked and secured in a storage facility with controlled temperature. Humidity in the room will be monitored. The room is accessible only to those individuals authorized by the PI.

Records will be made of the receipt and dispensing of the study drugs supplied. At the conclusion of the study, any unused study drugs (including placebo) as well as original containers (even if empty), will be retained by Celerion, returned to the Sponsor or designee, or destroyed, as per Sponsor instructions. If no supplies remain, this fact will be documented in the pharmacy product accountability records.

### **13.6 Data Handling and Record Keeping**

Celerion CRFs will be used. CRFs are printed directly from the ClinQuick® database. Each CRF is reviewed and signed off by the PI.

ClinQuick® is a fully integrated, study management and data capture system designed and built by Celerion for use in phase 1 clinical research centers. ClinQuick® will be used for all data that can be captured electronically via barcode or electronic acquisition (e.g., vital signs, meal times, blood draw times, etc.). Electronic changes will be traceable through computer capture.

Other data (e.g., medical history, inclusion/exclusion criteria, etc.) will be entered into ClinQuick® by remote data entry or via double data entry by 2 different associates using an automated verification system within ClinQuick®. AEs and concomitant medications will be entered into ClinQuick® by single data entry.

Visual and computerized methods of data validation will be applied in order to ensure accurate, consistent, and reliable data for the subsequent statistical analysis.

These procedures aim to detect out-of-range values, contradictory data, abnormal evolutions over time, and possible undetected protocol violations (eligibility criteria, time and medication compliance, etc.).

All raw data generated in connection with this study, together with the original copy of the final report, will be retained by Celerion until at least 5 years after the last approval of a marketing application in an ICH region and until there are no pending or contemplated marketing applications in an ICH region or at least 5 years have elapsed since the formal discontinuation of clinical development of the investigational product. These documents should be retained for a longer period, however, if required by the applicable regulatory requirements or by an agreement with the Sponsor. It is the responsibility of the Sponsor to inform the PI/Institution as to when these documents no longer need to be retained.

### **13.7 Report Format**

According to the ICH Harmonized Tripartite Guideline (Organization of the Common Technical Document for the Registration of Pharmaceuticals for Human Use M4 and the ICH M2 Expert Working Group), the final report will be written according to the ICH E3 Guideline (Structure and Content of Clinical Study Reports).

### **13.8 Protocol Amendments**

Any amendments to the study protocol that seem to be appropriate as the study progresses will be discussed between Sponsor and the PI or designee. All revisions and/or amendments to the protocol in writing must be approved by the Sponsor, the PI or designee, and the IRB before implementation.

### **13.9 Publication Policy**

All unpublished information given to Celerion by the Sponsor shall not be published or disclosed to a third party without the prior written consent of the Sponsor.

The data generated by this study are considered confidential information and the property of the Sponsor. This confidential information may be published only in collaboration with participating personnel from the Sponsor or upon Sponsor's written consent to publish the article.

## 1. INTRODUCTION

The following statistical analysis plan (SAP) provides the framework for the summarization of the data from this study. The SAP may change due to unforeseen circumstances. Any changes made from the planned analysis within protocol, after the unblinding, or locking of the database will be documented in the clinical study report (CSR). The section referred to as Table Shells within this SAP describes the traceability of the tables, figures, and listings (TFLs) back to the data. Note that the header for this page will be the one used for the main body of the CSR.

Any additional exploratory analyses not addressed within this SAP and/or driven by the data, or requested by Aronora, Inc., will be considered out of scope and must be described in the CSR.

## 2. OBJECTIVES AND ENDPOINTS

### 2.1 Objectives

The **primary objective** of the study is to assess the safety and tolerability of single intravenous (IV) bolus doses of E-WE thrombin when administered to healthy adult subjects.

The **secondary objective** is to assess the pharmacodynamics (PD) of single IV bolus doses of E-WE thrombin when administered to healthy adult subjects. The activated protein C/protein C inhibitor complex (APC-PCI) will be used as a surrogate biomarker for drug exposure.

### 2.2 Endpoints

The **primary endpoints** of the study will be the number and severity of treatment-emergent adverse events (TEAEs) following single IV bolus doses of E-WE thrombin and placebo. In addition, physical examinations, vital signs, electrocardiograms (ECGs), clinical laboratory tests (including coagulation), thrombin time, immunogenicity, and injection site reaction will be assessed throughout the study.

The **secondary endpoints** are the PD (i.e., APC-PCI) of E-WE thrombin following single IV bolus doses. PD will act as a surrogate for pharmacokinetics (PK) of E-WE thrombin.

## 3. STUDY DESIGN

This is a randomized, double-blind, placebo-controlled, single ascending dose (SAD) study conducted at one study center in the United States (US).

Four (4) cohorts of either 6 subjects (Cohort 1 [4 active and 2 placebo]) or 5 subjects (Cohorts 2, 3, and 4 [4 active and 1 placebo]) are planned for evaluation.

In each cohort, subjects will receive a single IV bolus of E-WE thrombin or placebo. Subjects will participate in only 1 cohort.

Cohort 1 will contain a sentinel group of 2 subjects (1 placebo and 1 active) who will be dosed at least 28 days before the remaining group of subjects. The remaining subjects in Cohort 1, and subjects in each of Cohorts 2, 3, and 4 will be dosed in 2 groups separated by at least 14 days (2 subjects in each group [Cohort 1] or 2 subjects in the first group and 3 subjects in the second group [Cohorts 2-4]). The placebo will be randomized to one of the groups.

Dose escalation to the next dose level (i.e., next cohort) will not take place until after the Principal Investigator (PI) has reviewed the safety data. If any findings in the safety data are of concern, then the Safety Review Committee (SRC) comprised of but not limited to, the Sponsor, medical monitor, and the PI will convene to determine if adequate safety and tolerability from the previous cohort has been demonstrated to permit proceeding to the next cohort. Data from all subjects in the cohort will be used and reviewed for a dose escalation decision and a minimum of 4 subjects must complete the study (up to Day 14) before proceeding to the next higher dosing cohort.

Subjects will participate in only one cohort. An attempt will be made to have at least 30% of the total subjects of a race/ethnicity minority group. An attempt will be made to include at least 2 females per cohort.

Safety (i.e., physical examinations, vital signs, ECGs, clinical laboratory tests [including coagulation], thrombin time, immunogenicity, injection site reaction, and AEs) will be assessed throughout the study.

Blood samples will be collected for PD assessment (i.e., APC-PCI) of E-WE thrombin.

Blood samples will be also collected for the ADA evaluation.

Subjects will be housed on Day -1, at the time indicated by the clinical research unit (CRU), until after the 24-hour blood draw and/or study procedures. At all times, a subject may be required to remain at the CRU for longer at the discretion of the PI or designee.

Subjects (including those who terminate early) will return on Days 14 and 28 for follow-up (FU) procedures (coagulation sample collection, thrombin time measurement, and immunogenicity sample collection) and to determine if any AE has occurred since the last study visit). Subjects who terminate the study early will be asked to continue aPTT and thrombin time monitoring as scheduled until Day 28.

Any subjects for whom aPTT and/or thrombin time did not reach  $\pm 10\%$  of the baseline value or within the normal range by Day 14, will return every 7 days ( $\pm 2$  days) until aPTT and thrombin time reach  $\pm 10\%$  of the baseline value or within

the normal range and for a FU visit (i.e., FU procedures and AE evaluation listed on Day 28 will be repeated) 7 days ( $\pm$  2 days) after it was reached.

The total planned duration of subject participation is approximately 56 days from screening to last FU.

## 4. ANALYSIS POPULATIONS

### 4.1 Analysis Populations

**Safety population:** All subjects who received the study drug (active or placebo) will be included in the safety summary.

**PD population:** All subjects receiving the study drug (active or placebo) and having any measurable PD data will be included in the PD data set. The Sponsor will assess the real time aPTT on-site. The protein C samples will be processed by Celerion associates and then shipped to Aronora for later analysis.

### 4.2 Preliminary Data and Interim Analysis

If there are safety concerns, all available blinded safety/tolerability data (i.e., physical examinations, ECGs, vital signs, clinical laboratory tests [including coagulation], thrombin time, injection site reaction, and AEs available for all subjects who have completed up to Day 14 procedures) will be reviewed by the SRC prior to dose escalation.

At the Sponsor's request, unblinded safety tables, figures, and data listings may be presented to the sponsor's medical expert and head of regulatory for the purposes of planning the next initial Phase 2 studies prior to database lock. These interim analyses will be performed on data that will be edit-checked and monitored.

A safety programmer and a biostatistician at Celerion who are not involved with the present study will be unblinded to prepare the required unblinded safety tables, figures, and data listings. All the personnel related to the present study will remain blinded.

## 5. TREATMENT DESCRIPTIONS

E-WE thrombin will be supplied as sterile, non-pyrogenic, preservative-free liquid for IV administration. E-WE thrombin will be supplied as 0.1 mg/mL for IV use and given as a single IV bolus, according to the planned dose (mcg/kg) for each cohort, as noted Table 5.1. Matching placebo will be supplied as sterile formulation buffer for injection via IV route.

**Table 5.1 Dosing Duration**

Dose Level	Manual Push Time
Cohort 1: 0.5 mcg/kg	~ 15 seconds
Cohort 2: 1.0 mcg/kg	~ 15 seconds
Cohort 3: 2.0 mcg/kg	~ 30 seconds
Cohort 4: 4.0 mcg/kg	~ 1 minute

Dose levels will be used in the presentation of tables, figures, and listings. Dose levels will be described as proposed in Table 5.2 below:

**Table 5.2 Description of Dose Levels**

Dose Level	Abbreviated Description
0.5 mcg/kg	0.5 mcg/kg E-WE thrombin (IV bolus)
1.0 mcg/kg	1.0 mcg/kg E-WE thrombin (IV bolus)
2.0 mcg/kg	2.0 mcg/kg E-WE thrombin (IV bolus)
4.0 mcg/kg	4.0 mcg/kg E-WE thrombin (IV bolus)
Pooled Placebo	Placebo Solution (IV bolus)

**Note:** The planned dose levels described above may be revised up or down or a dose level may be repeated based upon data from a previous dose level, however, doses will not exceed 4.0 mcg/kg without a protocol amendment.

## 6. PHARMACODYNAMIC ANALYSIS

There will be 5 dose levels consisting of 4 active drug and 1 pooled placebo. The placebo subjects from all dose levels will be pooled into a single placebo group for all summaries and presentations.

Individual, mean, and median data will be presented graphically for all dose levels as well as pooled placebo group.

Additional analyses may be performed as deemed necessary upon review of the data.

### 6.1 APC-PCI

APC-PCI values will be listed and presented graphically.

Plasma for APC-PCI will be collected at predose, 0.083, 0.25, 0.5, 1, 2, 4, and 24 hours postdose. The sample times and Hour 0 are in relation to start of IV bolus.

Sample analysis for APC-PCI will be performed by Celerion (Lincoln, NE).

## **6.2 Real-Time aPTT**

Blood samples for real-time aPTT will be analyzed by Aronora on site. Samples will be collected in blood collection tubes containing 3.2% sodium citrate by a Celerion employee and transferred directly to an Aronora employee for sample processing as per their internal procedures.

At the end of the study, platelet poor plasma samples obtained by centrifugation of citrated blood will be shipped to the Sponsor for their internal analyses.

Blood samples for the assessment of real-time aPTT will be collected at predose, 0.083, 0.25, 0.5, 1, 2, 4, and 24 hours postdose.

Data for real-time aPTT will not be analyzed by Celerion.

## **6.3 Protein C**

Blood sample for the assessment of protein C will be collected at the following timepoints: predose, 1, 2, and 24 postdose. The protein C samples will be processed by Celerion associates and then shipped to Aronora for their internal analyses.

Data for protein C will not be analyzed by Celerion.

## **6.4 Data Summarization and Presentation**

All PD markers will be tabulated by dose level and a pooled placebo group. Summary statistics, including the number of observations (n), arithmetic mean (mean), standard deviation (SD), coefficient of variation (%CV), minimum, median, and maximum will be computed.

The level of precision will be presented as follows: n will be presented without decimal, mean, SD, minimum, median, and maximum will be presented to 1 decimal place. All percentages will be presented to 1 decimal place.

## **7. IMMUNOGENICITY**

Plasma and serum samples for immunogenicity testing will be collected on Days -1, 14, and 28. If ADA are detected on Days 14 and 28, the check-in sample on Day -1 will be also evaluated. ADA detection will be reported and summarized.

Assessment of ADA will be performed by Haemtech Biopharma Services, Inc.

For samples with a positive confirmatory assay, titers of ADA will be presented with the same level of precision as received from the bioanalytical laboratory. A table will be provided for ADA positive duration for each dose level, where duration is defined

as the time interval between the first postdose and last postdose occurrence of positive ADA.

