**Tables 14.2.2.1 and 14.2.2.2 will be in the following format.**

Table 14.2.2.1 Plasma Anti-E-WE Thrombin Antibody Detection Following Administration of a Single IV Dose of 0.5, 1.0, 2.0, or 4.0 mcg/kg E-WE Thrombin Summary by Collection Time and Treatment - Number of Subjects (% Total Subjects)

Test	Result	0.5 mcg/kg				1.0 mcg/kg			
		Day X	Day X	Day X	Overall*	Day X	Day X	Day X	Overall*
		N=X	N=X	N=X	N = X	N=X	N=X	N=X	N = X
Initial	Negative	X (X%)	X (X%)	X (X%)	X (X%)	X (X%)	X (X%)	X (X%)	X (X%)
	Positive	X (X%)	X (X%)	X (X%)	X (X%)	X (X%)	X (X%)	X (X%)	X (X%)
Confirmatory	Negative	X (X%)	X (X%)	X (X%)	X (X%)	X (X%)	X (X%)	X (X%)	X (X%)
	Positive	X (X%)	X (X%)	X (X%)	X (X%)	X (X%)	X (X%)	X (X%)	X (X%)
Neutralizing	Negative	X (X%)	X (X%)	X (X%)	X (X%)	X (X%)	X (X%)	X (X%)	X (X%)
	Positive	X (X%)	X (X%)	X (X%)	X (X%)	X (X%)	X (X%)	X (X%)	X (X%)

N is the total number of subjects dosed at each dose level.

Programmer Note:

- Immunogenicity sampling times: Day -1, Day 14, and Day 28
- Treatments:
  - 0.5 mcg/kg E-WE thrombin (IV bolus)
  - 1.0 mcg/kg E-WE thrombin (IV bolus)
  - 2.0 mcg/kg E-WE thrombin (IV bolus)
  - 4.0 mcg/kg E-WE thrombin (IV bolus)
  - Pooled Placebo: Placebo Solution (IV bolus)

Note: \* if the response of a subject is positive at least once postdose, it will be counted as "positive"; otherwise will be considered as "negative".

Only screening positives will be reassayed for confirmatory analysis.

Program: /AAXXXXX/ECR/sas\_prg/pksas PROGRAMNAME.sas DDMMYYYY HH:MM

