**Tables 14.2.2.5 and 14.2.2.6 will be in the following format.**

Table 14.2.2.5 Anti-E-WE Thrombin Antibody +Duration by Dose Level Following Administration of a Single IV Dose of 0.5, 1.0, 2.0, or 4.0 mcg/kg E-WE Thrombin

E-WE Thrombin	Subject	Duration*
0.5 mcg/kg	X	X Days
	X	X Days
1.0 mcg/kg	X	X Days
	X	x Days

Programmer note:

[figure not shown]
- Treatments:
  - 0.5 mcg/kg E-WE thrombin (IV bolus)
  - 1.0 mcg/kg E-WE thrombin (IV bolus)
  - 2.0 mcg/kg E-WE thrombin (IV bolus)
  - 4.0 mcg/kg E-WE thrombin (IV bolus)
  - Pooled Placebo: Placebo Solution (IV bolus)

Note: \* duration is defined as the time interval between the first postdose and last postdose occurrence of positive ADA. If positive ADA is only on Day 28 the duration will be N/A.

Note: Figures of 14.2.3 and In-text Figure 11-1 will be in the following format.

Figure 14.2.3.1

[figure not shown]
Mean <Matrix Analyte> Concentrations Versus Time  
(Linear Scale)

Program: /CAXXXXX/sas\_prg/pksas/adam\_meangraph.sas DDMMMYYY HH:MM  
Program: /CAXXXXX/sas\_prg/pksas/meangraph.sas DDMMMYYY HH:MM

Figure 14.2.3.2

Median <Matrix Analyte> Concentrations Versus Time  
(Linear Scale)

[figure not shown]
Program: /CAXXXXX/sas\_prg/pksas/adam\_meangraph.sas DDMMYYYY HH:MM  
Program: /CAXXXXX/sas\_prg/pksas/meangraph.sas DDMMYYYY HH:MM

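### On the scheduled visits, ADA duration can only be 0 days, 14 days or N/A, and the two numbers are observed minimums printed as durations

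*SAP*

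**What the plan says.** SAP section 7 gives the schedule: "Plasma and serum samples for immunogenicity testing will be collected on Days -1, 14, and 28". The programming note for detection Tables 14.2.2.1 and 14.2.2.2 lists the same days: "Immunogenicity sampling times: Day -1, Day 14, and Day 28". Each subject therefore has two scheduled post-dose results.

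Section 7 defines duration "as the time interval between the first postdose and last postdose occurrence of positive ADA". The shell shared by Tables 14.2.2.5 (plasma, anti-E-WE thrombin) and 14.2.2.6 (serum, anti-WT thrombin) repeats the definition in a footnote and adds a rule that is not in section 7: "If positive ADA is only on Day 28 the duration will be N/A". The shell prints one number of days per subject, by dose level. Neither place calls the value a minimum or marks a subject whose last sample is still positive.

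SAP section 3 also plans conditional sampling. Subjects whose aPTT or thrombin time has not recovered by Day 14 return about weekly until it has. They then have one more visit about 7 days later, at which "FU procedures and AE evaluation listed on Day 28 will be repeated". The Day 14 and 28 follow-up comprises "procedures (coagulation sample collection, thrombin time measurement, and immunogenicity sample collection", so that extra visit includes an ADA sample. Neither section 7 nor the shell mentions it.

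**The concern.** With two scheduled post-dose samples, the interval from first to last positive is fixed by the visit calendar and says little about how long antibody persists. A subject still positive at the last sample is right-censored, and onset before Day 14 is not observed. Even so, the shell prints a plain number of days. A confirmed positive on Day 14 alone is shown as 0 days.

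What is at stake is how the immunogenicity results are read. The two tables cover antibodies to the drug and to wild-type thrombin in a first-in-human study. A column holding only 0, 14 and N/A could be taken to mean that responses are short, which these samples cannot show.

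**Working it through.** The plan states no duration figure to reproduce, so the check lists every possible result pattern.

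**Inputs.** Scheduled post-dose days 14 and 28 (SAP section 7 and the detection shell); duration = day of last post-dose positive − day of first post-dose positive (section 7); N/A if positive only on Day 28 (duration shell); dosing on Day 1. The bounds on the true duration assume one continuous positive episode that starts after dosing. Days are nominal.

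**Scheduled visits**

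| Day 14 | Day 28 | Section 7 formula | Shell prints | True duration |
|---|---|---|---|---|
| + | − | 14 − 14 = 0 | 0 days | above 0, below 28 − 1 = 27 days |
| + | + | 28 − 14 = 14 | 14 days | at least 14 days, no upper limit |
| − | + | 28 − 28 = 0 | N/A | above 0, no upper limit |

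Three things follow.

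1. The printed set is 0, 14 and N/A. Both numbers are lower limits. Two of the three positive patterns are still positive at the last scheduled sample, and neither is marked as ongoing.
2. The rule is inconsistent for single positives. The section 7 formula gives 0 for any single positive sample. The shell keeps 0 if that sample is on Day 14 and replaces it with N/A if it is on Day 28.
3. A subject positive on Day 14 with a missing Day 28 sample also gets 0, the same entry as a subject shown to be negative on Day 28. The first has no upper limit and the second does.

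**With the repeat follow-up visit** (7 days after coagulation values recover, nominal)

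| Recovered | Repeat visit | First positive Day 14, last at repeat | First positive Day 28, last at repeat |
|---|---|---|---|
| Day 21 | Day 28 | 28 − 14 = 14 | 0 (single day) |
| Day 28 | Day 35 | 35 − 14 = 21 | 35 − 28 = 7 |
| Day 35 | Day 42 | 42 − 14 = 28 | 42 − 28 = 14 |
| Day 42 | Day 49 | 49 − 14 = 35 | 49 − 28 = 21 |

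Other values therefore become possible if these samples count. The N/A rule names Day 28 only, so a subject first positive at a Day 35 repeat visit would get 35 − 35 = 0 days. The same kind of result on Day 28 gets N/A.

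**The case against.** The best case for leaving the plan as it is has four parts.

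- **The definition is printed under the table.** A careful reader can see that the number is an interval between positive samples, and the shell contains no mean, median or test that would carry a censored value further. This is fair, and it limits the harm. It does not turn 0 or 14 into a duration, and nothing in the row tells the reader who was still positive.
- **N/A is not a false number.** This stands. A reader might count the Day 28-only rule as a wrong result, but N/A only says that no duration is available. The faults are that it hides an ongoing response and departs from the section 7 formula.
- **Other displays carry the information.** This is partly right. The detection tables and in-text Tables 11-3 and 11-4 give results by day, and a subject counts as positive overall "if the response of a subject is positive at least once postdose", so no Day 28 positive disappears from the report. But those tables give group counts, and the titer shell (Tables 14.2.2.3 and 14.2.2.4) lists subjects without a time column. The listing index in SAP section 10.3 names a plasma anti-E-WE antibody listing and no serum anti-WT one. For serum anti-WT antibody, Table 14.2.2.6 is the only listed by-subject display of timing.
- **Extra sampling is planned for suspected cases.** This also stands. A reader might infer that duration can never be anything but 0, 14 or N/A. The repeat visit in SAP section 3 rules that out, so the limit applies to the scheduled visits. The visit also exposes a gap, because the SAP does not say whether its samples count.

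**Conclusion.** The point holds for the scheduled visits. There the tables can print only 0 days, 14 days or N/A, and the two numbers are observed minimums shown as durations. The 0 could stand for anything up to just under 27 days when Day 28 is negative, and the 14 for any duration of 14 days or more. These bounds rest on one continuous episode starting after the Day 1 dose and on nominal days; actual dates could move the 14 slightly. The inconsistent handling of single positives needs none of these assumptions.

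The importance is low. The tables are descriptive lists of antibody-positive subjects in a study of 21 planned subjects. Two stronger readings are not supported. A reader might link the tables to the stopping rules in protocol section 10.4.1.4, but those turn on the presence of antibody, and no stopping or escalation decision uses its duration. A reader might also suppose that a Day 28-only subject is the one most likely to have a persisting response. The documents give no basis for that, and a subject positive on both days is equally positive at the last scheduled sample.

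**What to change.** Amend SAP section 7 and the shell shared by Tables 14.2.2.5 and 14.2.2.6 as follows:

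1. Rename the value *observed minimum duration*.
2. Show each positive subject's pattern: Day 14 only with Day 28 negative; Day 14 only with Day 28 missing; Day 28 only; both days.
3. If the last available sample is positive, print *ongoing at last sample, at least x days*, with x taken from actual sample dates.
4. Apply one rule to every single positive sample, whichever visit it falls on, and state it identically in section 7 and the footnote.
5. State that repeat follow-up samples are included, and extend the pattern to cover them.

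The cost is a revised definition and a small change to one shell and its program. No new samples, visits or data are needed.
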